- 1. Describe the change in symptom burden in sub-acute (Part A) and acute (Part B) concussion for the two groups.** This aim defines our primary objective. In Part A we will enroll a maximum of 30 subjects in the open-label treatment Arm (OXE-103) but will stop recruiting when that arm has 20 participants who have completed study requirements. All Part A participants must be diagnosed with a concussion and experience persistent concussion symptoms \leq 28 days post injury. The Part A non-treatment concurrent control Arm will enroll a minimum 20 participants who complete the study requirements, but may continue to recruit more than 20 participants while the Part A open-label treatment Arm is still recruiting. In Part B we will enroll a maximum of 50 subjects but will stop recruiting after each arm (OXE-103 Arm and placebo Arm) has 20 participants who have completed the study requirements. In Part A subjects will receive OXE-103 open-label and in Part B we will randomize 1:1 to placebo versus OXE-103. The Post-Concussion Symptom Score questionnaire (PCSS) will be used as an overall measure of symptom burden. The number of symptoms and severity at each time point are also measures of interest. In addition, subjects will be asked to identify and rank the 4 most bothersome symptoms. We hypothesize that changes in these most bothersome symptoms may have a higher correlation to improvement in quality of life. A visual comparison of change in the two groups will be made. We will consider a change of 20% to be clinically meaningful. Our primary aim will describe the change in symptoms between day 1 and day 15.
- 2. Describe the change in quality of life between the two groups.** This aim defines one of our secondary objectives. To assess this, we will administer the Quality of Life after Brain Injury scale (QOLIBRI) and a Patient Global Assessment of Status (PGAS). A change of 20% will be considered clinically meaningful. Our primary objective with this aim will assess the change between days 1 and 15.
- 3. Describe the correlation between the change in symptom burden and quality of life.** This is an exploratory aim. We hypothesize that improvement in symptom burden will correlate with improvement in quality of life measures. This may be more evident in the correlation between the change in the 4 most bother symptoms and quality of life measures. This aim will describe this correlation between days 1 and 15.

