Significant abnormalities in serum creatinine (>2.5 mg/dL), or alanine aminotransferase (ALT) or aspartate aminotransferase (AST) >3 times the upper limit of normal, or bilirubin (>2.5 mg/dL) will exclude subjects from participation.

Subjects with any abnormal findings noted on imaging, such as hemorrhage, will be excluded from the study. Subjects who meet criteria for moderate or severe TBI will also be excluded.

Subjects who are known to be pregnant will be excluded. Subjects who do not agree to double-barrier contraception or abstinence (for female subjects of child-bearing potential or male subjects who are sexually active with a female of child-bearing potential) until the day following last dose (total of at least 5 half-lives) will be excluded.

In Part A subjects receiving other concomitant medications, physical therapy, or other treatments related to their current mTBI will be eligible if they meet the inclusion criteria. Subjects (or household members) who are not able to inject themselves or the subject will be excluded. Ultimately study subject participation will be at the discretion of the study physician.

For both Part A and Part B, subjects are not allowed to be concurrently enrolled in another therapeutic intervention clinical trial while participating in this study. Any subjects currently enrolled in such a separate therapeutic intervention clinical trial, for any condition, will be excluded from participating in this study. For clarification, this does not include observational clinical trials or registries.

Procedures and labs performed as part of the subject's normal medical care (not for study) within one day prior to consent may be allowed to be used for study. This includes items such as CBC, CMP, ECG, and pregnancy testing.

Study Procedures:

General study design:

We propose an open-label design for the sub-acute Part A. Arm 1 will receive OXE-103 and Arm 2 will be a non-treatment concurrent control. Both Arms of Part A will each have a target of 20 subjects who will complete the study requirements. In Arm 1 (open-label treatment) an additional 10 subjects may be enrolled to replace any subjects that do not complete the study requirements. In the event that Arm 2 (non-treatment control) has reached its minimum target of 20 completed subjects and Arm 1 (open-label treatment) is still recruiting, then Arm 2 may continue to enroll subjects until Arm 1 reaches its target enrollment.

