In Part B the design will be randomized, double-blinded, and placebo-controlled with Arm 1 receiving OXE-103 and Arm 2 receiving placebo. The enrollment target will be 20 subjects receiving OXE-103 and 20 subjects receiving placebo. Up to 50 subjects may be enrolled in Arms 1 and 2 combined to allow for replacement of subjects who may not complete the study requirements.

In Part A Arm 1 and Part B both Arms 1 & 2, the maximum enrollment will be 80 subjects. For the Part A Arm 2 (non-treatment concurrent control) the minimum target enrollment will be 20 subjects, but there will be no maximum number.

We will randomize using the REDCap database. The database will be set up to share randomization allocation only with the statistician and Investigational Pharmacy. All subjects will be consented and either begin treatment within 24 hours of presentation to the Trauma Unit (for Part B) or ≤ 28 days post-injury (for Part A). For Part A, starting on Day 1, the treatment cohort (Arm 1) will receive OXE-103 40ug/kg twice daily by self-injection and the non-treatment control group (Arm 2) will begin their monitoring. For Part B, on Day 1 (within 24 hours of being admitted into the Trauma Unit) the treatment Arm will receive OXE-103 40ug/kg SC twice daily by self-injection and the placebo Arm will receive a placebo injection SC twice daily. OXE-103 and placebo will be maintained and dispensed by Investigational Pharmacy. Subjects will receive an 8-day supply of syringes pre-loaded with OXE-103 or placebo. Each cohort receiving OXE-103 or placebo will receive the 2nd set of syringes with OXE-103 or placebo at the Day 8 visit. Appropriate therapy that would be considered standard of care by the Principal Investigator or Co-Investigator will be administered or prescribed at any time during subjects' study participation.

Subject training

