Outcomes for the investigation of the effect of OXE-103 will be based on self-reported symptom scoring, quality of life questionnaires, computerized cognitive testing assessing executive function, memory and processing speed, and accelerometer-based balance scoring. Safety assessments will include collection of adverse events, clinical laboratory samples, electrocardiograms (ECGs), vital signs including body weights, suicide screening and physical/neurological examination findings.

3. Study Objectives

The primary objective of this study is to describe the change in symptom burden of subacute or acute concussion for the two treatment groups in each part, as measured by the change from baseline to Day 15 in the Post-Concussion Symptom Score questionnaire (PCSS) total score, total number of symptoms and total score for the 4 most bothersome symptoms (4MBS, as identified on Day 1). Improvements of $\geq 20\%$ will be considered clinically meaningful.

The secondary objectives are to:

- Describe the change in quality of life for the two groups in each part as measured by the change from baseline to Day 15 in the Quality of Life after Brain Injury (QOLIBRI) total score and Patient Global Assessment of Status Visual Analog Scale (PGAS VAS).
- Describe changes in cognitive performance for the two groups in each part as measured by the change from baseline to Day 15 in the BrainCheck composite score.

Exploratory objectives of the study are to:

- Describe the correlation between the change in symptom burden and quality of life during the treatment period for each group in each part.
- Describe changes in symptom burden and quality of life at different time points for the two groups in each part.

4. Sample Size

The exploratory nature of this study is such that it is not powered to yield statistically significant outcomes, but will allow detection of trends within subjects and between groups within each part, will support comparison with standard tests of neurocognitive functions, and will provide sample size estimates for future studies of individuals with acute or persistent concussion related symptoms.

The study will enroll a maximum of 50 subjects in each part, but may stop recruiting if each group has at least 20 participants who have completed the study.

5. Outcome Measures

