6.1 General Methods

This pilot study will describe changes observed in the two treatment groups, placebo versus OXE-103, separately for each part. Since the study is exploratory, analyses will focus on descriptive comparative statistics and not on a pre-specified statistically significant primary endpoint. Data will be used to enable power calculations and the definition of suitable clinical endpoints for further clinical development. Data from baseline and on Study Days 4, 8, 11, 15, 21, and 44 will be analyzed. Note that day definitions in this study will follow the Clinical Data Interchange Standards Consortium in that there is no Day 0;

assessments performed prior to randomization will be done on Days -7 and -3 (Part A only) and randomization is considered Day 1.

For all evaluations of changes from baseline, baseline is defined as the last reported value before the first dose of study drug. In most instances, this will be the value recorded on Day 1.

For the evaluation of safety, a treatment-emergent finding is any result that is newly reported after the first dose of study drug. This may include an existing condition which worsens in severity after the start of treatment.

Continuous variables such as total score or change from baseline will be summarized by the number of observations, mean, standard deviation, median, minimum and maximum value. Graphs of changes from baseline over time will present the means and 95% confidence intervals.

Binary or categorical variables will be summarized by the number of observations in each category along with the percent of observations.

To aid in interpretation of the importance of relationships, correlation coefficients (Pearson and Spearman) will be reported with p-values.

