6.8 Efficacy Analysis

As described previously, binary variables (responders) and continuous variables (values and changes from baseline) will be summarized with appropriate descriptive statistics for each treatment group and each visit (as needed). Changes from baseline over time will also be presented graphically with means (95% confidence intervals) with both treatment groups presented on the same figure.

To evaluate the appropriateness of the current responder definitions, a Receiver Operating Characteristic (ROC) analysis will be performed for each response outcome measure. The current definitions indicate that a ≥20% improvement over baseline is required for a subject to be considered a responder. In the ROC analysis, the percent improvement will be varied from 5% to 95% to determine which percentage is best for distinguishing OXE-103 treated subjects from placebo subjects. If data suggest an early treatment response, the ROC analysis may be performed for a time point earlier than Day 15.

FDA pre-IND guidance from the FDA on the clinical development of OXE-103 advised that “***The outcome measure should be constructed in a way that ensures that a score change is indicative of a meaningful improvement in how a patient feels or functions that comes from a treatment effect specific to mild TBI.***” Pearson and Spearman correlation coefficients (and p-values) will be calculated to examine

relationships between the PCSS changes and changes in the quality of life measures (QOLIBRI total score and PGAS VAS).

Relationships between PCSS changes and changes in cognition and balance (BrainCheck composite measure) will also be examined using correlation coefficients.

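### The SAP sets the symptom/quality-of-life correlation by arm within part, names no level in 6.8 and plans no combined estimate; one arm-stratified coefficient per part would be about 30% more precise

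*Protocol*

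**What the plan says.** Protocol, Specific Aims, Aim 3, is exploratory: "Describe the correlation between the change in symptom burden and quality of life". It adds the hypothesis "We hypothesize that improvement in symptom burden will correlate with improvement in quality of life measures" and fixes the period: "This aim will describe this correlation between days 1 and 15". It gives no level of analysis. Aims 1, 2 and 5 refer to the two groups; Aim 3 does not.

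SAP section 3 supplies a level in its exploratory objective: "Describe the correlation between the change in symptom burden and quality of life during the treatment period for each group in each part". SAP 6.8, which gives the method, says "Pearson and Spearman correlation coefficients (and p-values) will be calculated to examine" the relation of PCSS changes to changes in QOLIBRI and PGAS. It names neither arm nor part. SAP 6.1 keeps the parts apart ("This pilot study will describe changes observed in the two treatment groups, placebo versus OXE-103, separately for each part") and says that p-values accompany the coefficients to help judge how important a relationship is. SAP 6.13 plans no modelling and no covariate adjustment. No combined or arm-adjusted correlation appears in either document.

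On numbers, the protocol's general study design says for Part A "Both Arms of Part A will each have a target of 20 subjects who will complete the study requirements", and for Part B "The enrollment target will be 20 subjects receiving OXE-103 and 20 subjects receiving placebo".

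**The concern.** These correlations have a specific job. SAP 6.8 places them directly after the FDA's pre-IND advice that a score change should reflect a meaningful improvement in how a patient feels or functions. Both documents also say the pilot's data will help define endpoints for later trials. Whether PCSS change tracks quality-of-life change is therefore among the more useful things this study can report.

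Read with SAP section 3, the plan reports that relationship only in cells of about 20 subjects, each with its own p-value. Two arms with the same underlying relationship can then show visibly different coefficients, one significant and the other not. A reader could take this as evidence that the symptom score is meaningful in one arm only. An estimate using both arms of a part, while keeping the comparison within arm, would describe the relationship more precisely from the same data.

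**Working it through.** **Inputs.** The protocol targets 20 completers per arm, hence 40 per part. The numbers analysed may differ: efficacy uses the per-protocol set (SAP 6.2), and Part A Arm 2 has no maximum. The documents give no expected correlation, so the true r is an assumption, shown at 0.3, 0.5 and 0.7. The 5% two-sided level is used only to label p-values. The plan states no precision or power for Aim 3, so there is no figure to reproduce.

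**Intervals.** On the Fisher z scale, the 95% interval is tanh(atanh(r) ± 1.96 × SE).

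- One arm: SE = 1/√(20 − 3) = 0.243.
- Two arms combined on the z scale: SE = 1/√(17 + 17) = 0.171.
- Partial correlation given arm (each change minus its arm mean): SE = 1/√(40 − 3 − 1) = 0.167.

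At r = 0.5, atanh(r) = 0.549:

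- One arm: 0.549 ± 0.475 gives 0.07 to 0.77, width 0.70.
- z-combined: 0.549 ± 0.336 gives 0.21 to 0.71, width 0.50.
- Partial: 0.549 ± 0.327 gives 0.22 to 0.70, width 0.49 from unrounded limits.

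The reduction in width is 1 − 0.50/0.70 = 29% or 1 − 0.49/0.70 = 30%.

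| Assumed r | One arm, n = 20 | Two arms, z-combined |
|---|---|---|
| 0.3 | −0.16 to 0.66 | −0.03 to 0.57 |
| 0.5 | 0.07 to 0.77 | 0.21 to 0.71 |
| 0.7 | 0.37 to 0.87 | 0.49 to 0.83 |

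**Chance disagreement between arms.** This was simulated with 50,000 pairs of arms of 20, bivariate normal, with the same true r in both. With 18 degrees of freedom, p < 0.05 needs an observed |r| above 0.444.

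| Assumed r | One arm reaches p < 0.05 | Exactly one of two does | Coefficients differ by ≥ 0.3 | Opposite signs |
|---|---|---|---|---|
| 0.3 | 25% | 38% | 31% | 17% |
| 0.5 | 64% | 46% | 23% | 2% |
| 0.7 | 96% | 8% | 9% | 0.04% |

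The third column agrees with 2p(1 − p): at r = 0.5, 2 × 0.644 × 0.356 = 0.459, against 0.457 simulated. That expression peaks at 50% when p = 0.5, which happens at a true r of about 0.44. The figure at 0.5 is therefore near the worst case.

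**Why not simply pool the raw data.** If both changes differ between arms by d standard deviations, a within-arm correlation ρ becomes (ρ + d²/4)/(1 + d²/4) in the raw pooled data. With d = 0.8, d²/4 = 0.16: ρ = 0 becomes 0.16/1.16 = 0.14, and ρ = 0.5 becomes 0.66/1.16 = 0.57. Stratifying by arm removes this.

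**Number of coefficients.** If all three PCSS measures are used, by-arm reporting at one time point gives 3 PCSS × 2 quality-of-life × 2 coefficient types × 4 arms = 48 coefficients, each with a p-value.

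**The case against.** The strongest defence is that by-arm correlation is a sound choice: it stops an arm difference in means from manufacturing a correlation. This matters most in Part A, where Arm 2 takes subjects who decline the drug or fail screening for it, Arm 1 is open-label and both measures are self-reported. A common relationship is least secure there. The aim is also exploratory, the study is stated to be unpowered, and no decision depends on a p-value. Finally, a reader could combine the two Pearson coefficients unaided, so little information is truly lost. All of this stands, and it limits the point to an inexpensive improvement. It does not remove the gap: an arm-stratified estimate keeps the same protection, and a planned estimate is better than one a reader must build.

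Stronger readings are tempting, but the documents do not support them:

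- *That Aim 3 asks for a single correlation which the SAP contradicts.* Aim 3 is silent on level. The SAP fills that silence, and SAP section 1 says the SAP prevails where the two differ.
- *That the SAP allows by-arm coefficients only.* That wording is in the objective. SAP 6.8 states no level, and SAP 5.3 leaves relationships between outcomes open. The defect is an unstated level and a missing estimate, not a prohibition.
- *That the arms will disagree.* This depends on the true r, which is not given. At 0.7 disagreement in significance falls to 8%. High values are plausible for PGAS, whose question is itself about the effect of symptoms.
- *That the split halves the data.* This is so only within a part and only at equal arm sizes, which Part A need not have.

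**Conclusion.** The point holds as a gap in specification with a modest, inexpensive remedy. SAP section 3 implies cells of about 20, SAP 6.8 does not say at what level its coefficients are computed, and no combined estimate is planned. An arm-stratified estimate per part would narrow the 95% interval by roughly 30%. Significance would split between arms by chance alone in about 38% to 46% of trials at a true r of 0.3 to 0.5, but in only 8% at 0.7.

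These figures assume 20 analysed subjects per arm, approximate bivariate normality and the same true correlation in both arms. The last assumption is reasonable in randomised Part B and weakest in Part A.

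**What to change.** In SAP 6.8:

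- State that the coefficients are computed by arm within part.
- Add, for each part, one arm-stratified (pooled within-arm) correlation with a 95% interval. One way is to combine the arm-specific Pearson, and likewise Spearman, coefficients on the Fisher z scale: z = Σ(nₖ − 3)zₖ / Σ(nₖ − 3), with SE = 1/√Σ(nₖ − 3) for Pearson. The weights allow for unequal arms. This SE is the Pearson one, so the SAP should name the variance or bootstrap used for Spearman.
- Keep the by-arm coefficients alongside, and state that a difference between arms in p-values will not be interpreted.
- For Part A, state that the combined value is read together with the by-arm values and is not the main estimate.

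In SAP 6.13, note that this stratification by arm is the exception to no adjustment. When revising, redefine the groups in Part A: SAP section 2 still describes randomisation to placebo, whereas the current protocol has open-label treatment and a non-treatment control.

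The cost is a few lines of text and one further column with its interval per correlation table (3 × 2 × 2 × 2 parts = 24 estimates at one time point). No new data are needed. The downside is the assumption of a similar relationship in both arms, which the retained by-arm values let a reader check, though only roughly at these numbers.

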	
(ASBI 301 (n=6), ASBI 303 (n=6), ASBI 304 (n=17), NA 1401(n=42), NA 1501(n=12) and NA 1502 (n=6).
 
Additional data from studies referenced in 5.3 above:
 
In addition to the data referenced above, serum samples for GH and IGF-1 was also assessed in ASBI 307 n=142. Additional PD markers not mentioned above were also assayed across the 9 studies include: prolactin n=72, ACTH n=72, cortisol n=214, catecholamines n=89, insulin n=89, glucose n=225, A1C n=159, FSH n=12, LH n=12, CRP n=165, NT-proBNP n=6, IL-6 n=159, IL-1B n=17, TNF n=159.
 
GH consistently increased proportional to the dose of OXE103; IGF-1, prolactin, and ACTH either showed increases which returned to baseline within 3 hours of dosing or showed no difference to placebo; the remaining PD markers showed no changes attributed to administration of OXE103.
 
The conclusions across the 9 studies were that no safety issues related to these biomarkers and the administration of OXE103 was observed.
 
5.4.2.1 Overall safety Evaluation:
 
glucose tolerance testing was done in studies ASBI 304 (n=17) and ASBI 307 (n= 151) since it has been reported that ghrelin can suppress insulin release and cause insulin resistance [Garin et al. 2013]. No obvious relationship was observed between 2-hour postload value from OGTT (mmol/L; Day 8) and predicted AUC_{ss} (pg·h/mL; Day 85) of OXE103.
 
Appendix 1: Tabular Summaries of OXE103 NonClinical Studies:
 
GH Secretion, Non-GLP, Study PBC 79-44 (n=4M): OXE103 did not significantly increase plasma prolactin and ACTH concentrations

[figure not shown]
Safety Concern	Safety Data
Published Studies	
There is extensive published literature on over 100 clinical studies administering ghrelin via intravenous infusion or bolus. The patient populations in these studies include: Healthy, obese, gastrectomy, cancer, hypopituitarism, metabolic syndrome/diabetes, anorexia nervosa/ bulimia nervosa, pulmonary disease, gastroparesis, hyperthyroid, renal disease, heart failure, cushing's syndrome, PCOS, functional dyspepsia, acromegaly, hyperparathyroid, osteoarthritis, and major depression disorder. Garin et.al 2013 (reference supplied upon request).
 
These studies support the benign safety profile of OXE103 and are consistent with data generated in the Phase 1 and Phase 2 clinical studies.

PART A: POST-ACUTE DAY 1

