Subjects will be provided with instructions for SC self-administration of OXE-103 and placebo. Subjects will be trained to inject themselves and need to demonstrate competency by self-administering the first dose of the study drug at the study site. Alternatively, if a subject is accompanied by a reliable and willing household member, that individual will be trained to administer study drug to the subject and will be required to demonstrate competency at the study site. If neither self-administration nor administration by a household member is feasible the subject will be deemed ineligible to participate. Subjects will also be instructed on storage of the drug/placebo according to the parameters. A study team member will document the storage location for each subject enrolled. Subjects will be asked to inject the first daily dose in the morning, after eating. The second dose will occur in the evening, again after eating. The study team may provide injection diaries to subjects in order to document dosing.

Recruitment:

Subject recruitment for Part A will take place among patients seen in [name] for Concussion Management (CCM) clinic located at The University of Kansas Health System (TUKHS), Landon Center on Aging, Department of Neurology. Subject recruitment for Part B will take place among patients seen by the TUKHS Trauma team. Patients meeting the study's

inclusion/exclusion criteria will be invited to participate in the study. If they are interested, a study team member will meet with the patient to discuss the study in more detail. Informed consent will be sought; when obtained, subjects will be screened for study risks and other exclusion criteria. Subjects enrolled in Part B of the study by the Trauma team will be followed after discharge from the hospital in [name] clinic; the remainder of their study visits will be completed with [name] in his ambulatory clinic. Part A Arm 1 (non-treatment control) study visits may be conducted via telemedicine at the discretion of the Principal Investigator, [name], with the exception of Study Days 1 and 15 when correlative labs will need to be drawn, and Day 44 when study iPads will need to be returned to the study team.

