Subjects will undergo laboratory testing at Day 1 with a complete metabolic profile (CMP), to include liver function and glucose, and complete blood count (CBC). Significant abnormalities in serum creatinine (>2.5 mg/dL), or alanine aminotransferase or aspartate aminotransferase >3 times the upper limit of normal, or bilirubin >2.5 mg/dL will exclude subjects from participation. Study team will collect CBC and CMP (with fasting glucose, fasting when possible) at visits 2 through 4 to monitor for any changes during treatment. If there are any clinically significant abnormal values that have not yet corrected, labs will be repeated at 7-day intervals until they normalize. Additional serum will be taken with each laboratory sample for correlative testing of sparse PK sampling and anti-ghrelin antibody and biomarker testing at study visits 1-5. Subjects enrolled in the Part A Arm 2 non-treatment control group will have these correlative lab samples taken at Days 1 and 15.

Outcomes & Study Tools:

Symptom reduction (AIM 1): Our primary goal is to describe the change in number of symptoms and/or severity in acute and sub-acute concussion with treatment with OXE-103 using the PCSS at Days 1 and 15. We will also collect data at Days 21 and 44 to potentially describe long term changes and potential lasting effect (AIM 4).

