5.4 Safety Outcome Measures

Any laboratory, vital sign or ECG result meeting Common Terminology Criteria for Adverse Events (CTCAE), version 5.0, will be included in adverse event (AE) reports. Any unexpected findings on physical or neurological examinations will also be included in AE reports.

- Occurrence of any AEs commonly reported for OXE-103, CTCAE Grade 1 (mild) only.
- Occurrence of any unanticipated or unexpected (UU) treatment-emergent (TE) AE, UU serious AE (TE-SAE), UU AE leading to study drug discontinuation (TE-DAE), UU TE-AE related to study drug and UU TE-AE classified as Grade 2 or higher according to CTCAE, version 5.0. [Note that any AE commonly reported for OXE-103 that has CTCAE Grade 2 (moderate) or higher will be included among the UU TE-AEs.]
-
- Change from baseline in clinical laboratory parameters at each post-baseline assessment (Days 8, 15 and 21)
- Change from baseline in vital signs (including body weight) at each post-baseline assessment (Days 8, 15 and 44)
- Change from baseline in ECG intervals at each post-baseline assessment (Days 8, 15, 21)
- Change from baseline in Patient Health Questionnaire (PHQ)-9 total score at each post-baseline assessment (Days 8, 15 and 44)

6. Statistical Methods

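### Glucose change from baseline mixes sampling conditions: no fasting condition at Day 1, fasting only where possible at follow-up, and fasting status unused, so a drug effect could be masked or exaggerated

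*Protocol*

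**What the plan says.** The protocol's Laboratory and Endocrine Risks section sets two sampling conditions for one analyte. At entry, "Subjects will undergo laboratory testing at Day 1 with a complete metabolic profile (CMP), to include liver function and glucose" is required, with no mention of fasting. For follow-up, "Study team will collect CBC and CMP (with fasting glucose, fasting when possible) at visits 2 through 4", and the stated purpose is "to monitor for any changes during treatment". Visits 2 to 4 are Days 8, 15 and 21 in the schedules of events.

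Under Inclusion/Exclusion, procedures and laboratory tests from normal care "within one day prior to consent may be allowed to be used for study". The metabolic panel is among the examples, again with no fasting condition.

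SAP 6.1 says "baseline is defined as the last reported value before the first dose of study drug", which it expects to be Day 1 in most instances. SAP 5.4 lists "Change from baseline in clinical laboratory parameters at each post-baseline assessment (Days 8, 15 and 21". SAP 6.9 summarises values and changes by treatment group and visit, and SAP 6.13 rules out covariate adjustment. Fasting is not mentioned in the schedules or anywhere in the SAP.

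Two further passages bear on Day 8, the only laboratory visit after Day 1 that falls within dosing. Subject training says "Subjects will be asked to inject the first daily dose in the morning, after eating". The schedule footnote requires Day 1 and Day 8 assessments to precede dispensing, not the morning dose; the list of changes gives dosing before the Day 8 visit as the reason for that wording.

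**The concern.** A change from baseline can be read as a drug effect only if both samples are taken under comparable conditions. By asking for fasting samples at follow-up, the protocol accepts that fasting matters for glucose, but it sets no matching condition at baseline.

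Glucose is a relevant analyte for this drug. The protocol's safety table explains earlier glucose tolerance testing by noting that "it has been reported that ghrelin can suppress insulin release and cause insulin resistance". If the mix of fed and fasting samples differs between Day 1 and follow-up, the mean change contains a component unrelated to the drug. If fasting status is not recorded, nobody can later say how large that component was or which way it went.

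**Working it through.** The documents give no glucose mean, SD, effect size or fasting share, so there is no plan figure to reproduce. The text establishes the mixed conditions; the arithmetic below only illustrates the consequences.

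**Assumed inputs (none is in the documents)**
- D = fed minus fasting glucose: 10 to 30 mg/dL
- g, f = fasting shares at Day 1 and at follow-up; f - g varied from -0.25 to +0.5
- r = true drug-related rise: 10 mg/dL
- SD of change without mixing: 12 mg/dL

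**Within one arm**

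Offset = -D × (f - g). Observed mean change = r + offset. Each cell gives the offset, then the observed change when r = +10 (mg/dL).

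| f - g | D = 10 | D = 20 | D = 30 |
|---|---|---|---|
| +0.50 | -5; +5 | -10; 0 | -15; -5 |
| +0.25 | -2.5; +7.5 | -5; +5 | -7.5; +2.5 |
| 0 | 0; +10 | 0; +10 | 0; +10 |
| -0.25 | +2.5; +12.5 | +5; +15 | +7.5; +17.5 |

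A rise is fully masked when D × (f - g) is at least r. Equal shares give no bias. More fasting at Day 1 than at follow-up exaggerates a rise.

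**Part A**

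The Arm 2 schedule has no metabolic panel, and the Safety Monitoring paragraph exempts that arm. No comparator removes the offset from the Arm 1 change.

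**Part B**

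Both randomised arms follow the same schedule. With the same f and g in each arm, the expected difference is (r - D(f - g)) - (0 - D(f - g)) = r. The cost is noise:

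SD of change = √(12² + D² × [f(1 - f) + g(1 - g)]), taking fasting status as independent between visits.

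With f = 0.75 and g = 0.25 the bracket is 0.1875 + 0.1875 = 0.375:
- D = 10: √(144 + 37.5) = 13.5
- D = 20: √(144 + 150) = 17.1
- D = 30: √(144 + 337.5) = 21.9

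At 20 per arm the 95% half-width of the difference is 1.96 × SD × √(2/20). It rises from 7.4 mg/dL without mixing to 8.3, 10.6 and 13.6 mg/dL.

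**Yield of a same-status comparison**

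Suppose 20% of Day 1 and 70% of follow-up samples are fasting, independently. Same-status pairs are 0.8 × 0.3 + 0.2 × 0.7 = 0.24 + 0.14 = 38%, about 8 of 20. Fasting-fasting pairs are 14%, about 3 of 20.

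**The case against.** The strongest reply is that the direction is unknown. A reader might infer that baselines are mostly fed and follow-ups mostly fasting, so that a rise would be hidden. The documents do not support this. They give no fasting share at any visit, the follow-up request is permissive, and a subject who took the morning dose as instructed before the Day 8 visit has eaten. That objection stands, and the point is limited to an uncontrolled shift of either sign.

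A reader might also infer that the within-arm change is the only glucose evidence in Part A. It is not. SAP 6.9 also summarises values, SAP 5.4 sends results meeting CTCAE criteria to the adverse event reports, and the protocol repeats clinically significant abnormal tests weekly until they resolve. A marked individual rise would surface. These outputs are themselves affected by unrecorded fasting status, but they do not need a matched baseline.

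The stakes are moderated too. The safety table reports no obvious relationship between post-load glucose and drug exposure, and lists glucose (n=225) and A1C (n=159) among markers with no change attributed to the drug. Known diabetes is an exclusion. Those studies did not enrol concussion patients, however. Part A Arm 1, without a laboratory comparator, would be weak causal evidence even with perfect fasting.

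The fasting request and the dosing instruction are not strictly incompatible: a draw before breakfast and before the morning dose satisfies both. The Day 8 footnote does not require that order, though. Case report forms are not among the documents, so meal status may be captured there; neither document asks for it or uses it.

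Finally, this is a descriptive, unpowered pilot and glucose is not a named endpoint. That limits the importance of the point, but a descriptive change table still needs comparable samples.

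**Conclusion.** The point holds as a defect in comparability. Followed as written, the plan yields a glucose change that mixes sampling conditions and can mask or exaggerate a drug effect. Under the assumed gap and difference in shares, the offset is about +7.5 to -15 mg/dL, so a true +10 mg/dL could appear as anything from +17.5 to -5 mg/dL. These figures rest wholly on assumptions; the documents fix neither sign nor size.

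It matters most in Part A Arm 1. In Part B the between-arm contrast is unbiased in expectation, provided fasting shares do not differ by arm, but it is less precise. The documents do not support the stronger conclusion that the plan hides a glucose rise or leaves Part A without other glucose information. This is a modest weakness in one safety summary, worth correcting because the correction is cheap and fasting status cannot be reliably recovered later.

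**What to change.** - **Data capture:** record fasting status, time of last meal and time of last dose with every metabolic panel, including Day 1 and any routine-care sample used as baseline.
- **SAP 5.4 and 6.9:** keep the planned glucose table. Add glucose values by fasting status at each visit, and change from baseline for pairs of samples with the same status. As supportive summaries, add same-status contrasts of Day 8 and Day 15 against Day 21, which is about a week after dosing ends.
- **Protocol:** the sponsor should reconcile the fasting request in Laboratory and Endocrine Risks, the instruction in Subject training to dose after eating, and the Day 8 schedule footnote.

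The cost is one case report form item and a few SAP lines, with no extra draw or visit. The same-status table may hold well under half of the subjects, so it should supplement the planned table, not replace it. The contrasts with Day 21 can show only effects that persist to the time of the draw: the protocol gives a half-life of 30 minutes, and a fasting morning sample comes many half-lives after the previous evening's dose.
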